Multidisciplinary behavioral therapy reduces rumination

NCT05232097

Study protocol with statistical analysis plan 2024-9-10

Study protocol with statistical analysis plan

Background

Rumination is a disorder of the gut-brain interaction characterized by repetitive regurgitation of ingested food that is followed by remastication and swallowing or spitting but without preceding retching or nausea (1, 2). The Rome IV rumination criteria include symptom onset six months prior to diagnosis and persistent symptoms for the last three months (3). Rumination is caused by subconscious but volitional contractions of the abdominal muscles resulting in intragastric pressure peaks of ≥ 30 mmHg that can be detected by performing esophageal high-resolution manometry using a solid test meal (4).

Biofeedback can reduce rumination by teaching the patients to control abdomino-thoracic muscle activity by following electromyography during eating. This has been proven in both open and randomized, placebo-controlled studies (5-6). Behavioral therapy consisting of diaphragmatic breathing exercises has been shown to reduce rumination in an open setting (7). We have used habit-reversal therapy with diaphragmatic breathing exercises successfully at our center to treat patients with supragastric belching (8). Our case report shows that rumination could be reduced by combining diaphragmatic breathing with abdomino-thoracic muscle relaxing exercises performed by a physiotherapist (9).

Data from randomized studies show that multidisciplinary therapy performed by a group comprising gastroenterologists, dietitians, hypnotherapists, psychiatrists and biofeedback physiotherapists is superior to standard gastroenterologist therapy in improving symptoms, psychological state, quality of life and costs in functional gastrointestinal disorders. The difference maintains up to 12 months of follow-up (10, 11).

We wanted to test the efficacy of a multidisciplinary, behavioral approach in treating patients with rumination in the present study. This study was approved by the Ethics Committee of Helsinki University Hospital (HUS/2118/2021) and by the Helsinki University Hospital Abdominal Center (HUS/23/2022). The study was registered at Clinical Trials as study number NCT05232097.

Objective

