The primary objective was a reduction of ≥ 2 of the rumination score measured by question 32 of the Rome IV diagnostic questionnaire for adult functional disorders (Rome IV) at baseline and at the 6-month control. Secondary objectives were improvement of HRQoL and functional capacity scores, reduction of anxiety and depression scores, and disappearance of intragastric pressure peaks in esophageal manometry at the 6-month control.

Patients

We recruited rumination patients from gastroenterology outpatient clinics to our study at the Helsinki University Hospital during the study period of Jan. 1, 2022, to Dec. 31, 2023.

The inclusion criteria for the study included age between 15-70 years, Finnish as the native language, fulfillment of the clinical Rome IV rumination criteria, a rumination score of ≥ 6 in the Rome IV diagnostic questionnaire for adult functional disorders (rumination occurring most days a week),

previous gastroscopy, esophageal manometry and MII-pH. We aimed to recruit patients, who had previously had esophageal manometry performed with intragastric pressure increases ≥ 30 mmHg immediately preceding the rumination experienced by the patient, suggestive of rumination. Patients with only a clinical diagnosis of rumination syndrome were also accepted in the study, because previous to our study, Nutridrink instead of a solid meal was used when performing standard esophageal manometry in our institution and thus might not always detect rumination.

The exclusion criteria comprised large hiatal hernia, severe esophagitis, previous fundoplication, eating disorder, BMI under 14, pregnancy, significant cognitive disorder, and any other condition hindering outpatient visits.

Study protocol

At the baseline visit, cases were checked to ascertain whether they fulfilled the inclusion or exclusion criteria. Previous conditions, investigations, use of medications, and symptoms were registered. All patients obtained written information about the study, about the behavioral and functional nature of rumination, and its therapy including diaphragmatic breathing exercises and thoracic and abdominal muscle relaxations. Written consent was obtained from all patients.

From the baseline visit the patients were referred to the speech therapist for five one-hour sessions, and to the physiotherapist for two one-hour sessions and to the psychologist's and the dietitian's consultation.

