Symptoms, HRQoL, depression, anxiety, and functional capacity were evaluated by questionnaires given to the patients and weight were defined at onset of the study and at the 6-month control. Esophageal manometry with a pancake meal (191 kcal) was performed at the 6-month control. The study protocol is displayed in the figure below (Figure 1).

Questionnaires

Symptom severity was evaluated by the Rome IV questionnaire for adult functional disorders (12). The question 32 of the Rome IV diagnostic questionnaire for adult functional disorders scores the rumination frequency as follows: "In the last 3 months, how often did food come back up into your mouth after you swallowed it ?, 0 = never, 1= fewer than 1 day a month, 2 = 1 day a month, 3 = 2-3 days a month, 4 = 1 day a week, 5 = 2-3 days a week, 6 = most days, 7 = every day, 8 = multiple times per day or all the time".

Depression was evaluated by the Beck Depression Inventory (BDI), anxiety by the Beck Anxiety Inventory (BAI), HRQoL by the 15D, a 15-dimensional measure of health-related quality of life and functional capacity by the World Health Organization disability assessment schedule 2.0 (WHODAS 2.0) (13-16). The patients filled out the questionnaires at home and mailed them to the hospital.

Behavioral therapy

The therapy comprised psychoeducation about the nature of rumination as a behavioral disorder and means of dealing with the symptom including diaphragmatic breathing exercises and guided eating performed by the speech therapist, and mind-body oriented physiotherapy, all aiming at habit reversal.

The patients were first taught the mechanisms of rumination at the speech-therapist visits. We considered it essential for the study's success for the patients to understand the functional nature of rumination. The next step was to teach them diaphragmatic breathing and to relax abdominal muscles. Finally, the patients were trained to apply these exercises during meals and to continue them at home.

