The patients were referred to a dietitian trained in functional behavioral disorders for psychoeducation, to evaluate food and meal and related mental threats, and to ensure a sufficient diet. The primary goal of the dietitian's psychoeducation was to ensure that patients did not have negative expectations regarding food or nutrients. It is common in functional diseases that patients develop learned experiences and expectations that become self-predictive. The dietitian interviewed the patients to discover which food products the patients avoided due to them provoking rumination or other gastrointestinal symptoms such as diarrhea, to learn if rumination played a role in managing anxiety, and to discern if the patients had lost weight prior to or during the study. No special diet instructions or foods were recommended to be avoided due to rumination. The dietary goal was to normalize eating.

Statistical analysis

SPSS software was used to perform the statistical analysis. The question 32 of the Rome IV diagnostic questionnaire for adult functional disorders was used for the sample size calculation. The hypothesis was that the mean (\pm standard deviation) self-perceived frequency of rumination at baseline would be 6 ± 2 (most days a week) because this was the inclusion criteria for the study and the symptom improvement after therapy would be ≥ 2 resulting in the score of 4 ± 2 (once a week) at the 6-month control. Using the Sample Size Calculator of ClinCalc.com the number of patients required was 8 to obtain 80% power and significance of $P < 0.05$. The non-parametric Wilcoxon's signed rank test and Mann-Whitney test for the analysis of related samples were used for the

comparison of differences in the distributions of variables between the baseline and the 6-month control except for the 15 dimensions of HRQoL which were analyzed by the paired samples t-test. The independent samples t-test was used to compare the mean 15D results of the patients at baseline with those of age-standardized general Finnish population. Apart from the manometry and 15D results which are displayed as means and standard deviations, all other results are displayed as medians and interquartile ranges.

Figure 1.

References

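### If manometry is compared before and after therapy, the comparison may mix the therapy effect with a change of test meal, because the earlier tests may have used Nutridrink and the 6-month test used a pancake meal

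*Combined protocol and SAP*

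**What the plan says.** All references are to the combined protocol and SAP.

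- **Background:** rumination produces intragastric pressure peaks of at least 30 mmHg, which "can be detected by performing esophageal high-resolution manometry using a solid test meal".
- **Objective:** the secondary objectives include "disappearance of intragastric pressure peaks in esophageal manometry at the 6-month control".
- **Patients:** an earlier manometry is an inclusion criterion, with no limit on how long before entry it was done. On its result: "We aimed to recruit patients, who had previously had esophageal manometry performed with intragastric pressure increases ≥ 30 mmHg". A positive test was not required, however: "Patients with only a clinical diagnosis of rumination syndrome were also accepted in the study". The reason given is that, before the study, "Nutridrink instead of a solid meal was used when performing standard esophageal manometry in our institution and thus might not always detect rumination".
- **Study protocol:** "Esophageal manometry with a pancake meal (191 kcal) was performed at the 6-month control". The assessments made at both times are listed separately: "questionnaires given to the patients and weight were defined at onset of the study and at the 6-month control". Manometry is not in that list.
- **Statistical analysis:** nonparametric tests are assigned to the "comparison of differences in the distributions of variables between the baseline and the 6-month control", with only the 15D dimensions excepted. Manometry results are to be shown as means and standard deviations. The section does not say of which quantity, or whether a before-after manometry test is intended.

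No text describes a pancake-meal manometry before therapy, an adjustment for the meal, or a restriction to patients tested twice with the same meal. Figure 1, which displays the study protocol, is not available in the text reviewed.

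**The concern.** Disappearance implies an earlier measurement. The only pre-therapy manometry in the text is a previous clinical examination, and this centre's standard test before the study used a provocation that the plan itself regards as less able to detect rumination. The plan raises the meal only to justify eligibility and does not return to it for the outcome.

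Manometry is the only outcome among the objectives that is not a questionnaire score. In a single-group study, readers will look to it to corroborate the self-reported result. If the two tests used different meals, a patient without peaks on Nutridrink can show them on the pancake meal without having worsened. In a patient with peaks on both, a real fall can be masked. A before-after difference or P value would then measure therapy and meal together.

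**Working it through.** **The plan's own figure.** The only calculated figure is the sample size of 8, for question 32 of the Rome IV questionnaire. With SD 2, difference 2, two-sided 0.05 and 80% power, the one-sample normal formula gives n = (2 × (1.960 + 0.842) / 2)² = 7.85, rounded up to 8. It reproduces and does not depend on manometry. No figure is stated for manometry, so the rest uses assumed values.

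**Share of patients with peaks.** Suppose every patient truly has peaks before therapy. Let a be the probability that a Nutridrink test detects them, b the probability that a solid-meal test does, and e the true share whose peaks vanish with therapy. Then:

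- share with peaks before = a
- share with peaks at 6 months = b × (1 − e)
- observed change = b × (1 − e) − a
- change with the solid meal at both times = b × (1 − e) − b

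| a | b | e = 0: before → after (change) | e = 0.5: before → after (change) | e = 0.5, solid meal both times |
|---|---|---|---|---|
| 0.5 | 0.9 | 50% → 90% (+40) | 50% → 45% (−5) | −45 |
| 0.5 | 1.0 | 50% → 100% (+50) | 50% → 50% (0) | −50 |
| 0.7 | 0.9 | 70% → 90% (+20) | 70% → 45% (−25) | −45 |
| 0.7 | 1.0 | 70% → 100% (+30) | 70% → 50% (−20) | −50 |
| 0.9 | 0.9 | 90% → 90% (0) | 90% → 45% (−45) | −45 |
| 0.9 | 1.0 | 90% → 100% (+10) | 90% → 50% (−40) | −50 |

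With no therapy effect, the meal change alone gives 0 to +50 points. With a true 50% disappearance, the observed change lies between 0 and −45 points, against −45 to −50 points with matched meals.

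**Peak counts.** If Nutridrink provokes a fraction f of the peaks that a solid meal would, and therapy truly halves them, the observed ratio of 6 months to baseline is 0.5 / f: 0.50 at f = 1, 0.71 at f = 0.7, 1.00 at f = 0.5 and 1.67 at f = 0.3. The plan does not name peak count as an outcome. This line applies only if the means it intends to display are of that kind.

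**Disappearance among patients with earlier peaks.** If the two detections and the response are independent, the share without peaks at 6 months is 1 − b × (1 − e). Nutridrink detection does not enter. For e = 0 it is 0% at b = 1.0 and 10% at b = 0.9. For e = 0.5 it is 50% and 55%. The meal change does not create disappearance in these patients, but an imperfect second test can.

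**Direction.** The table ignores selection. If everyone enrolled had a positive earlier test, the share before would be 100%. With no therapy effect and b = 0.9, the change would be 90% − 100% = −10 points, an apparent benefit. The meal change and the selection pull in opposite directions.

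**The case against.** Several parts of the opposing case stand.

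- A reader might infer that every patient's earlier test used Nutridrink. The text says only that it was the centre's standard before the study. Recruitment ran through 2022 and 2023, so some patients may have had a solid-meal test. A pre-therapy solid-meal test in Figure 1 cannot be excluded either, although the Study protocol text makes it unlikely.
- A reader might infer that the plan prescribes a manometry P value. The Statistical analysis section speaks of variables in general and names manometry only for its display format. A stand-alone 6-month result is compatible with the text. The defect is partly that the plan leaves this open.
- A reader might infer that the manometry outcome says nothing about therapy. That goes too far. If the later meal is the more sensitive one, a peak-free pancake test in a patient with earlier peaks is not explained by the meal change.
- A reader might infer that the bias simply runs against the therapy. That is the tendency of the meal change taken alone. Seeking patients with an earlier positive test, with no control group, favours apparent disappearance by chance.

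The plan also discloses the Nutridrink limitation openly. None of this removes the core point: the plan does not prevent a comparison across different meals, and its general wording invites one.

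**Conclusion.** The concern holds in a conditional form. If the baseline versus 6-month comparison is applied to manometry, whether as peak counts, mean pressures or the share of patients with peaks, it mixes therapy with a change of test meal wherever the earlier test used Nutridrink. Under the assumed detection ranges, the meal alone could shift the share with peaks by 0 to +50 points, enough at the extreme to conceal a true 50% disappearance. These figures are illustrations, since the documents give no detection rates. The net direction of bias is uncertain. Disappearance in patients with documented earlier peaks survives the meal change but, without a control group, remains open to chance variation.

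One secondary objective is affected. The primary endpoint and the sample size of 8 are not. Confidence is medium, because the meal used for each patient is not documented and Figure 1 could not be seen.

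**What to change.** 1. Tabulate, for each patient, the test meal and date of the earlier manometry and whether it showed peaks of at least 30 mmHg.
2. Report the 6-month pancake manometry as a stand-alone descriptive result: the number with and without peaks of at least 30 mmHg.
3. State in the Statistical analysis section whether manometry is compared with an earlier test, and of which quantity means and standard deviations are shown. Compute no before-after difference or P value across different meals.
4. Limit any quantitative paired comparison to patients tested with the same type of meal both times.
5. Report disappearance only among patients with documented earlier peaks, stating the meal used in each test.

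This needs no new measurement, only details from existing records and changes of wording. Repeat testing with the earlier meal is not proposed. The document is dated 2024-9-10 and says that manometry was performed. Recruitment closed on Dec. 31, 2023, so the last 6-month control fell due around the end of June 2024, and an added session is very probably no longer possible. The cost is a more modest claim: few or no patients may remain in a paired manometry comparison.

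### The planned baseline of 6 ± 2 is impossible for eligible scores of 6 to 8, and the claim of 80% power with 8 patients rests on unstated inputs and apparently a large-sample formula; like-for-like power is about 68% (paired t) or 61% (exact signed-rank)

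*Combined protocol and SAP*

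**What the plan says.** The Statistical analysis section bases the sample size on question 32 of the Rome IV questionnaire, the item behind the primary objective ("The primary objective was a reduction of ≥ 2 of the rumination score measured by question 32"). It supposes that the mean score "at baseline would be 6 ± 2 (most days a week) because this was the inclusion criteria for the study", and that "the symptom improvement after therapy would be ≥ 2 resulting in the score of 4 ± 2 (once a week) at the 6-month control". From a web calculator it concludes that "the number of patients required was 8 to obtain 80% power and significance of" P < 0.05. It does not report the SD of the within-patient change, the correlation between visits, the sidedness or the calculator option.

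The Patients section sets the entry threshold: "a rumination score of ≥ 6 in the Rome IV diagnostic questionnaire for adult functional disorders". The Questionnaires section gives the top category of the item: "8 = multiple times per day or all the time".

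For the comparison of baseline with 6 months, the Statistical analysis section names Wilcoxon's "signed rank test and Mann-Whitney test for the analysis of related samples were used for the" comparison of distributions. I take the signed-rank test as the planned paired test. The section does not say whether its P value is exact or asymptotic.

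**The concern.** Two separate things look wrong.

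First, the baseline is justified by the entry rule, yet that rule excludes it. The planning text treats the lowest eligible score as the mean and attaches an SD that scores of 6 to 8 cannot have.

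Second, the power claim cannot be checked from the inputs given. For a paired comparison the SD of the change determines the sample size, and it is missing. The inputs that most directly give 8 use a formula that ignores the small-sample behaviour of both the t test and the signed-rank test.

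This is the document's only sample size justification. A reader will take it that, with 8 patients, a true 2-point fall had a 20% chance of being missed. Under the two-sided inputs that give 8, that chance is about 32% (t) or 39% (exact signed-rank).

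**Working it through.** **Inputs from the document.** Alpha 0.05 (sidedness not stated), power 80%, baseline 6 ± 2, 6-month score 4 ± 2, fall of at least 2 (all Statistical analysis); entry score at least 6 (Patients); item maximum 8 (Questionnaires).

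**Inputs assumed.** An SD of change of 2 and a two-sided test in the main case; normally distributed changes unless stated.

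**1. Feasibility of the baseline.** Eligible scores are 6, 7 and 8. If the mean is 6, every score is 6 and the SD is 0. Over all sets of 8 such scores, the largest sample SD comes from four 6s and four 8s: mean 7, SD = √(8 × 1²/7) = 1.07. An SD of 2 cannot occur.

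**2. Reproducing the stated 8.** The paired normal approximation is n = ((z₀.₉₇₅ + z₀.₈₀) × SD/fall)² = ((1.960 + 0.842) × 2/2)² = 7.85, rounded up to 8. Its power at n = 8 is Φ(√8 − 1.96) = 80.7%. So 8 is not an arithmetic slip. It is not a unique match: a one-sided 5% paired t test also needs 8 (75.4% at n = 7, 81.5% at n = 8). A two-group formula with SD 2 gives 16 per group and does not reproduce it.

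**3. Power with 8 patients, two-sided, fall 2, SD of change 2.**
- Paired t: noncentrality 2/(2/√8) = 2.83 on 7 degrees of freedom; power 68.1%.
- Exact signed-rank: rejects at W ≤ 3 (true size 2 × 5/256 = 3.9%); simulated power 61.0%.
- Asymptotic signed-rank: rejects at W ≤ 4 (nominal P = 0.0499, true size 2 × 7/256 = 5.5%); power about 68%.

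**4. Patients with both questionnaires needed for 80%.** Paired t: 9 give 74.8% and 10 give 80.3%. Exact signed-rank: 10 give about 78% and 11 give about 81%.

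**5. Sensitivity at n = 8, two-sided.**

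| Fall | SD of change | Paired t | Exact signed-rank |
|---|---|---|---|
| 2 | 1.5 | 90% | 85% |
| 2 | 1.6 | 86% | 80% |
| 2 | 1.73 | 80% | 74% |
| 2 | 2 | 68% | 61% |
| 2 | 2.24 | 59% | 52% |
| 2.5 | 2 | 86% | 80% |
| 2.5 | 2.24 | 77% | 71% |
| 3 | 2 | 95% | 92% |
| 3 | 2.24 | 90% | 85% |

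Here 2.24 = √(1² + 2²): baseline SD about at its ceiling, 6-month SD 2, correlation 0. With SD 2, 80% is reached at a fall of about 2.3 (t) or 2.5 (exact signed-rank).

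**6. Integer scores.** Ties lower the signed-rank figures. With every patient at 6, falling to 4 ± 2 on the 0 to 8 item, exact signed-rank power at n = 8 is about 53%, against 61% for continuous changes with the same mean and SD.

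**7. Does the infeasible baseline SD cause the gap?** Use SD of change = √(s₀² + s₁² − 2r·s₀·s₁) with s₁ = 2. Lowering s₀ from 2 to 1 raises paired t power at n = 8 from 41% to 59% at r = 0, from 51% to 68% at r = 0.25 and from 68% to 80% at r = 0.5. At r = 0.75 it stays at 93%. So it does not. The gap in step 3 comes from the normal approximation at n = 8.

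**The case against.** The strongest reply is that 8 may be enough. The hypothesis is a fall of at least 2, so 68% and 61% describe the smallest effect it allows. A mean of 7 falling to 4 satisfies both the stated fall and the stated final score. On the integer scale, with a 6-month SD of 2 and correlation 0, that case has 93% (t) or 86% (exact signed-rank) power. The document gives SDs of scores, not of changes; with baseline SD 1, 6-month SD 2 and correlation 0.5, the SD of change is 1.73 and the t test has 80%. A one-sided t test has 81.5%, though the one-sided exact signed-rank test has only about 76%. Nor does the plan specify exact P values. All of this stands, and it makes the power figures conditional. It does not supply the missing inputs or make 6 ± 2 possible.

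A reader might infer more than the documents support:
- *That the trial was underpowered.* The number enrolled is not given, and the SD of change is unknown.
- *That the planned means contradict each other once the baseline mean exceeds 6.* They do not, because a fall larger than 2 is allowed.
- *That the recorded baseline SD could not have been 2.* The limit applies to entry scores. Eligibility was verified at the baseline visit ("cases were checked to ascertain whether they fulfilled the inclusion or exclusion criteria"), while questionnaires were completed at home and mailed. The document does not say outright that the two scores are one measurement. The planning paragraph, however, takes its 6 ± 2 from the entry rule.

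**Conclusion.** The point holds in two parts. The planning baseline is impossible for eligible scores; this follows from the document alone. The 80% power claim is not supported as written. Under the two-sided inputs that reproduce 8, the methods suited to that size give power 12 points lower (t) or 19 points lower (exact signed-rank) than stated, and 2 or 3 more complete pairs would be needed. That second part rests on an assumed SD of change of 2, a fall of exactly 2, a two-sided test and normal changes. Over the falls and SDs tabulated, exact signed-rank power with 8 patients runs from 52% to 92%, so 8 may be short or adequate, and the text does not let a reader tell which. The matter concerns the stated requirement, not the power achieved. No estimate and no type I error rate changes. It is worth fixing because the figure is the only planning basis for the primary item.

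**What to change.** Restate the calculation as a paired one. Give a baseline mean and SD that scores of 6 to 8 can have, the assumed fall and the resulting final score, the assumed SD of the within-patient change with its source, two-sided alpha of 0.05, and the signed-rank test with exact P values. Replace the flat 80% with a range. Possible wording, to follow the stated baseline:

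*With 8 patients who return both questionnaires, the two-sided 5% exact Wilcoxon signed-rank test has about 52% to 85% power for a mean fall of 2 points if the SD of the change lies between 2.24 and 1.5, and about 85% to 92% for a mean fall of 3 points if it lies between 2.24 and 2. These figures assume normally distributed changes. Ties on the 0 to 8 item lower them; for example, power is about 53% if all patients start at 6 and fall to 4 ± 2.*

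The document is dated after the recruitment period ended, so this can be a correcting note rather than a rewrite of the historical rationale. It costs one paragraph and a less favourable stated power. It needs no added enrolment and no change to the analysis beyond specifying exact P values.

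### The stated 80% power with 8 patients is for rejecting no change; it is not the power for the primary objective of a fall of at least 2 points, which is also the fall assumed

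*Combined protocol and SAP*

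**What the plan says.** The Objective section states: "The primary objective was a reduction of ≥ 2 of the rumination score measured by question 32", from baseline to 6 months. It does not say whether the reduction is in the group mean, the group median or each patient's score, and it gives no required number of responders.

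The Statistical analysis section bases the sample size on the same question. It supposes that "self-perceived frequency of rumination at baseline would be 6 ± 2 (most days a week") and that "the symptom improvement after therapy would be ≥ 2 resulting in the score of 4 ± 2 (once a week"). From these inputs it reports that "the number of patients required was 8 to obtain 80% power" at a significance level of 0.05.

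The tests named for the score (Wilcoxon signed rank, with Mann-Whitney alongside) serve for the "comparison of differences in the distributions of variables between the baseline and the 6-month control". The score falls under the rule that "all other results are displayed as medians and interquartile ranges". No test against a change of 2 is planned. The SD of the within-patient change is not given.

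**The concern.** The number 2 appears in two roles. In the Objective section it reads as a threshold that the result should reach. In the sample-size paragraph it is the true effect supposed. When the supposed truth sits on a threshold, the estimate is about as likely to fall short as to reach it, and more patients do not help. An 80% figure printed beside the same question can then be taken as the chance of meeting the primary objective if therapy works as supposed. The design does not have that property.

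At stake is how the result is read. An observed fall a little under 2 would be unsurprising under the plan's own hypothesis and should not count against the therapy. The stated power would also mislead anyone who sizes a later study from this one.

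**Working it through.** **Inputs.** From the Statistical analysis section: mean 6 at baseline and 4 at 6 months (fall 2), SD 2 at each visit, significance level 0.05, power 80%, n = 8. From the Questionnaires section: whole-point scores from 0 to 8. Assumed here: an SD of change of 2. With SD 2 at both visits, the SD of change is √(4 + 4 − 8ρ), which equals 2 only if the correlation ρ is 0.5.

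**1. The plan's own figure.** One-sample, two-sided normal approximation against zero change:

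n = [SD × (1.960 + 0.842) / fall]² = [2 × 2.802 / 2]² = 7.85, rounded up to **8**.

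Power at n = 8: 2/(2/√8) − 1.960 = 2.828 − 1.960 = 0.868, and Φ(0.868) = **80.7%**.

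The one-sided version gives 6.18, so 7. Two independent groups need 16 per group. Only the first version returns 8, and its null hypothesis is no change.

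**2. Objective read as a threshold on the mean.** If the true mean fall is 2 and the estimate is symmetric about it, then P(observed mean fall ≥ 2) = 1 − Φ((2 − 2)/(SD/√n)) = 1 − Φ(0) = **50%**, at any n and any SD.

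Scores are whole points, so exact ties with 2 raise this a little. Changes were drawn from a normal distribution with mean 2 and SD 2 and rounded to whole points (400,000 samples of 8). This gives **53.5%** for the mean and **63.4%** for the median. The median figure depends on the SD of change: 59% at 2.83 (ρ = 0), 70% at 1.41 (ρ = 0.75) and 80% at 1.

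**3. Objective read per patient.** The chance that one patient falls by at least 2 is 50% on a continuous scale. With rounding it is Φ((2 − 1.5)/2) = Φ(0.25) = 59.9%. Binomial tails for 8 patients:

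| Required responders | 50% per patient | 59.9% per patient |
|---|---|---|
| at least 4 of 8 | 63.7% | 82.4% |
| at least 5 of 8 | 36.3% | 59.1% |

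For example, with 50% per patient, at least 4 of 8 is (70 + 56 + 28 + 8 + 1)/256 = 163/256 = 63.7%.

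**4. Power against no change for the planned test.** The normal approximation is optimistic at n = 8. The exact two-sided Wilcoxon test rejects when the smaller rank sum is at most 3; its level is 2 × 5/256 = 3.9%. By simulation with continuous changes:

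| SD of change | Paired t-test | Exact Wilcoxon |
|---|---|---|
| 2 (ρ = 0.5) | 68% | 61% |
| 2.83 (ρ = 0) | 41% | 35% |

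These Wilcoxon figures ignore the ties and zero changes that whole-point scores will produce.

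**The case against.** The strongest reply is that 2 points is simply the target effect and that a significant change from baseline is the criterion. Powering a test of no change at the target effect is ordinary practice, and the paragraph never calls 80% the chance of reaching a threshold. This reading is tenable, but the plan does not state it, and the Objective section puts the 2 points into the primary objective itself. If this is what was meant, saying so is most of the correction. Even then 80% does not hold for the Wilcoxon test on these inputs.

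A second reply is that the hypothesis is worded as at least 2, so the true fall may be larger. A larger fall would raise every probability above, but the figures entered are 6 and 4.

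A third is that the chance of success cannot be put at one figure. This stands. A reader might infer that the trial had only a 50% to 63% chance of success, or that a mean fall below 2 counts as failure. The documents support neither: they give no success rule, those percentages need a group-level reading, and the whole-point and median values also need an SD of change that is not stated. A reader might also infer that a fall of at least 2 must be demonstrated with confidence. No such test is planned.

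Finally, the document is dated after recruitment closed and is written in the past tense. Rewording the power statement changes no analysis and no enrolment, which limits the weight of the point.

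**Conclusion.** The point holds as a misattributed design property. The 80% is a normal-approximation figure for rejecting no change when the true fall is 2 and the SD of change is 2, a value inferred because it reproduces n = 8. It is not the power for the objective of a fall of at least 2, for which the plan gives neither a decision rule nor a power.

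Under the plan's own assumption, the chance of an observed mean fall of at least 2 is about one half. This needs only symmetry of the estimate. The whole-point figures (about 53% for the mean, 63% for the median) also need n = 8 and an SD of change of 2. A per-patient reading gives about 36% to 82% for at least 4 or 5 of 8, depending on the count and on how scores are modelled.

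The SD itself is uncertain. A baseline of 6 ± 2 is hard to reconcile with entry at 6 or more on a scale that ends at 8, so the conditional figures should be quoted with their condition.

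**What to change.** In the Statistical analysis section:

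- State that the primary test is the Wilcoxon signed rank test of question 32, baseline against 6 months, with no change as the null hypothesis.
- State that 2 points is the assumed effect and not a success threshold covered by the power statement. Do not present 80% as the power for the objective of a fall of at least 2.
- Add that, if the true mean fall is 2, the chance of an observed mean fall of at least 2 is about one half, so a fall slightly below 2 is not evidence of failure.
- Restate the power against no change with 8 patients as about 61% for the exact Wilcoxon test (68% for a paired t-test), conditional on an SD of change of 2, and say that this SD is an assumption.

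The cost is a few sentences and a less favourable stated power. No extra patients are needed.
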